The goals of the proposed study are to test the usability, feasibility and preliminary efficacy of the E-Scale with wheelchair users. Up to fifteen overweight or obese wheelchair users will be enrolled in a 13 week study that includes standard behavioral treatment (SBT) for weight loss that focuses on diet, physical activity, and behavioral strategies (e.g., goal setting, self-monitoring) to support lifestyle changes specifically for people with mobility impairments. The subjects will also be provided the E-scale to track their weight daily. The primary outcomes will be usefulness (subjective feedback from a survey about the program/E-scale), feasibility (accuracy and repeatable measurements from the E-scale) and efficacy (improvements in weight and other measures of health) of the weight loss program coupled with the E-scale at the end of 13 weeks. The results could inform the refinement of this technology to increase its applicability for wheelchair users to independently monitor their weight in their own homes while attempting to lose weight.

CS2.2**Select the category that best describes your research:**

Hybrid - includes aspects of BOTH types of research (check this option if your research is mainly social/behavioral but also involves specimen collection or blood draws to look at biological measures)

[\[reviewer notes→\]](#)**CS3.0 Name of the Principal Investigator:**

Note: Adjunct faculty of the University, including lecturers and instructors, are not permitted to serve as a PI or Faculty Mentor but may serve as co-investigators. Refer to [Chapter 4](#) on the HRPO website for more information.

CS3.1 Affiliation of Principal Investigator:

UPitt faculty member

If you chose any of the **Pitt options**, please indicate the specific campus:

[Main Campus - Pittsburgh](#)

If you chose the UPitt faculty member option, provide the PI's **University Faculty Title**:

Associate Professor

CS3.2 Address of Principal Investigator:

[name]
[name]

CS3.3 Recorded Primary Affiliation of the Principal Investigator:

U of Pgh | School of Health and Rehabilitation Sciences | Rehabilitation Science and Technology

CS3.4 Identify the School, Department, Division or Center which is responsible for oversight of this research study:

[U of Pgh | School of Health and Rehabilitation Sciences](#)

CS3.5 Telephone Number of Principal Investigator:

[contact]

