To determine the usefulness, feasibility and efficacy of the E-scale system coupled with a standardized behavioral treatment weight-loss intervention for overweight or obese wheelchair users.

1.2 Specific Aims: List the goals of the proposed study (e.g., describe the relevant hypotheses or the specific problems or issues that will be addressed by the study).

Aim 1. To investigate the usefulness and feasibility of the E-scale system and efficacy of the E-scale coupled with a weight-loss intervention to assist overweight or obese wheelchair users with losing weight.

Hypothesis 1a: The E-scale will be useful based on self-reported feedback from wheelchair users by more than 50% stating that the E-scale is easy to use, their preferred weight monitoring system, them feeling that they would use the E-scale if it was available for them to purchase.

Hypothesis 2b: The E-scale will be feasible by providing accurate (+/- 2 lbs. from a calibrated scale measurement) and repeatable (<3lbs difference from day-to-day) weight measurements and by the wheelchair users continuing to use the scale more than 70% of the days of the study.

Hypothesis 2c: The E-scale coupled with the weight loss intervention will demonstrate efficacy by wheelchair users having significant improvements in weight, abdominal girth, body fat percentage and score on the Self-Rated Abilities for Health Practices Scale (SRAHP).

1.3 Background: Briefly describe previous findings or observations that provide the background leading to this proposal.

Wheelchair users have about twice the prevalence of obesity than the general population. There is also very little or no technology to which they have access to measure their weight frequently in their homes. Research however, has shown that monitoring your body weight frequently (i.e. daily) yields significantly better weight loss and weight maintenance results. This research has never included wheelchair users because they have not had access to technology to be able to measure their weight daily. The E-scale was developed as a weight monitoring technology for wheelchair users and has been tested for precision and accuracy in the laboratory.

1.4 Significance: Why is it important that this research be conducted? What gaps in existing information or knowledge is this research intended to fill?

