2.3 Summarize the general classification (e.g., descriptive, experimental) and methodological design (e.g., observational, cross-sectional, longitudinal, randomized, open-label single-blind, double-blind, placebo-controlled, active treatment controlled, parallel arm, cross-over arm) of the proposed research study, as applicable.

This study will be experimental. It will be a 13 week longitudinal efficacy study.

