During the next 12 weeks, subjects will be asked to weigh themselves every day with the E-scale app and record their diet, exercise and weight every day with the LoseIt! app. The data that is reported in the LoseIt! app by the subjects will be monitored by the study team using the ascendapp for LoseIt!, which allows a "coach" to monitor all of the data submitted by a client. The weight loss curriculum involves weekly lessons for the participants to learn and practice things like counting calories and fat, reorganizing their kitchens, doing more cardio work around the house, etc. This curriculum was adapted from the Diabetes Prevention Program Group Lifestyle Balance (DPP GLB) curriculum at Pitt specifically for people with mobility impairments. The study team will send periodic emails with comments to the participants encouraging their progress and adherence to the protocol and lesson materials for that week. Every week at a pre-defined time, a group chat room will be conducted with all of the subject's and the research team invited to attend to go over the lesson for that week and to have a group discussion for the participants to share successes and difficulties with the group. The chat room will be hosted using Adobe Connect with the audio and video capabilities disabled. The link to the chat room for each week will be emailed to the subjects along with the lesson materials. The curriculum disbursement, progress emails, and chat rooms will be led by a dietitian/nutritionist with experience in leading group weight loss programs.

During the last week of the study (week 13). The subjects will be asked to come back to the lab in-person where their weight will again be measured using the roll-on scale. Their

abdominal girth and body-fat percentage will also be measured again. The SRAHP will be administered to the subjects again and they will also be given the final questionnaire, System Usability Scale (SUS), which will evaluate how they felt about the E-scale and some aspects of entire study. Any android devices that were loaned to the subjects during the study will be collected and the apps on their personal devices will be deleted if they wish. Over the next few days, the study team will visit all of the subject's homes to remove the E-scales or the participants can bring them with them to the lab.

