[\[reviewer notes→\]](#)

2.12 **Does this research study involve any type of planned deception?**

If Yes, you are required to request an alteration of the informed consent process (question 4.7)

* No

[\[reviewer notes→\]](#)

2.13 **Does this research study involve the use of UPMC/Pitt protected health information that will be de-identified by an IRB approved "honest broker" system?**

* No

[\[reviewer notes→\]](#)

2.14

Will protected health information from a UPMC/Pitt HIPAA covered entity be accessed for research purposes or will research data be placed in the UPMC/Pitt medical record?

* No

2.14.1

Will protected health information from a non-UPMC/Pitt HIPAA covered entity be obtained for research purposes or will research data be placed in the non-UPMC/Pitt medical record?

* No

[\[reviewer notes→\]](#)

2.15

Does this research study involve the long-term storage (banking) of biological specimens?

* No

[\[reviewer notes→\]](#)

2.16

Will research participants be asked to provide information about their family members or acquaintances?

* No

[\[reviewer notes→\]](#)

2.17

What are the main outcome variables that will be evaluated in this study?

Subjective feedback from the survey about the usefulness and participants' satisfaction with portions of the program and E-scale.

Accuracy and repeatability of the E-scale measurements

Weight change, abdominal girth change, body-fat percentage change and Self-Rated Abilities for Health Practices (SRAHP) change

2.18

Describe the statistical approaches that will be used to analyze the study data.

* Addressed below:

Since there is only one group, most outcome variables will be analyzed using summary statistics. Baseline and final measurements will also be analyzed using paired t-tests.

[\[reviewer notes→\]](#)

2.19

Will this research be conducted in (a) a foreign country and/or (b) at a site (e.g., Navajo Nation) where the cultural background of the subject population differs

substantially from that of Pittsburgh and its surrounding communities?

- * No

Note that copies of training records, licenses, certificates should be maintained in the study regulatory binder and are subject to audit by the Research Conduct and Compliance Office (RCCO).

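### Does Hypothesis 2c need a written rule for what happens if only some of its four efficacy outcomes improve significantly?

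*Combined protocol and SAP*

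**What the plan says.** Section 1.2 states under Hypothesis 2c how the E-scale with the weight loss programme is to be judged efficacious: "by wheelchair users having significant improvements in weight, abdominal girth, body fat percentage and score on the Self-Rated Abilities for Health Practices Scale". The aim above it is "to assist overweight or obese wheelchair users with losing weight". The abstract (CS2.1) puts efficacy among the primary outcomes in looser terms: "efficacy (improvements in weight and other measures of health) of the weight loss program".

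Section 2.17 gives the main outcomes on this side as "Weight change, abdominal girth change, body-fat percentage change and Self-Rated Abilities for Health Practices (SRAHP) change", with none marked as leading. Section 2.18 puts summary statistics first, because there is only one group, and then adds: "Baseline and final measurements will also be analyzed using paired t-tests". It gives no significance level, sidedness or rule for combining the four tests.

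Section 2.3 labels the work as follows: "It will be a 13 week longitudinal efficacy study". The abstract speaks of preliminary efficacy and of at most fifteen participants. Section 3.12 calls the study exploratory and reports that no sample size calculation was made.

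Hypothesis 1a sets a separate target for usefulness, to be met "by more than 50% stating that the E-scale is easy to use, their preferred weight monitoring system", followed by a third statement about willingness to use a purchased device.

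**The concern.** Efficacy is made to depend on significance, and significance is never defined. Four outcomes are tested and the plan is silent on partial success. If weight falls clearly but body fat or the Self-Rated Abilities for Health Practices (SRAHP) score does not move, one author could write that efficacy was not demonstrated, because the hypothesis names all four. Another could write that it was, because the aim concerns weight. That choice would be made with the data in view. At the extreme, counting any single significant outcome as success would inflate the chance of a false claim.

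Hypothesis 1a raises a smaller question of the same kind. One threshold covers three statements, with no stated denominator and no interval.

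**Working it through.** **Inputs.** From the documents: at most 15 participants (CS2.1, 3.11), four outcomes (1.2, 2.17), paired t-tests (2.18). They give no effect size, standard deviation, correlation or significance level. Assumed here: two-sided 5% per test, counted as success only in the direction of improvement; the same standardised change d on all four outcomes; correlation 0 to 0.7 between changes; all 15 complete. The plan has no figure of its own to reproduce.

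**One outcome.** The test has 14 degrees of freedom, critical value 2.145 and noncentrality d√15 = 3.873d. The power is 0.438 at d = 0.5, 0.821 at d = 0.8 and 0.949 at d = 1.0.

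**Four outcomes, independent.** With single-test power p, all four succeed with probability p⁴, and one to three succeed with probability 1 − p⁴ − (1 − p)⁴. At d = 0.8:
- All four: 0.821⁴ = 0.454.
- Mixed: 1 − 0.454 − 0.179⁴ = 1 − 0.454 − 0.001 = 0.545.

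**Four outcomes, correlation 0 to 0.7** (simulation, 200,000 runs per setting):

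| d | Weight significant | All four significant | One to three significant |
|---|---|---|---|
| 0.5 | 0.438 | 0.036 to 0.206 | 0.864 to 0.477 |
| 0.8 | 0.821 | 0.455 to 0.642 | 0.544 to 0.310 |
| 1.0 | 0.949 | 0.812 to 0.874 | 0.188 to 0.119 |

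The independent case agrees with the hand calculation. Mixed results are therefore quite possible. They become uncommon only when effects are large.

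**No true effect.** Weight alone gives a false improvement 2.5% of the time. Requiring all four gives at most 0.24%, reached at correlation 0.7. Counting any one would give 1 − 0.975⁴ = 9.6% if independent and about 7% at correlation 0.7, but no section of the plan supports that reading.

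**What each remedy would do** (n = 15, d = 0.8):
- Name weight as lead: power 82%, but false success rises from under 0.3% to 2.5%, and three outcomes lose their standing.
- Keep four and apply Holm: weight is called improved 70% to 73% of the time instead of 82%.
- Write that all four are required: this repeats what the *and* already says.

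**What is reported in any case.** Section 2.17 defines each outcome as a change, and 2.18 summarises them. From a mean change and its standard deviation (SD), the 95% interval is mean ± 2.145 × SD/√15, or ± 0.554 SD. A reader can form it for each outcome whichever rule is used.

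**Hypothesis 1a.** 8 of 15 is 53%, with exact 95% interval 27% to 79%. The denominator can matter: in an assumed case, 6 of 10 respondents is 60%, but 6 of 15 enrolled is 40%. Giving both counts settles this in the report.

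**The case for a change.** The strongest case for a change is that the wordings do not match. Hypothesis 2c asks for significant improvement in four named outcomes, the abstract for improvement in weight and unspecified other measures, and Aim 1 for weight loss. A study that calls itself an efficacy study, and lists efficacy among its primary outcomes, should fix in advance what would count. The remedy is a line or two and needs no new data. Weight is also a natural candidate for lead outcome, since participants return to the laboratory in the last week, "where their weight will again be measured using the roll-on scale". Dropout makes it worse: if only 10 completed (assumed), a mixed result at d = 0.8 would have a 47% to 83% chance.

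Much of this stands. The wordings do differ, the level is unstated, and the probabilities are right under their assumptions. What does not follow is that the plan must be altered. The abstract's phrase is a summary, and it does not offer a rival rule such as any one of four. A mixed result is troublesome only for someone who departs from the plain meaning of the hypothesis. And because there is no control group, a significant fall in weight under a sharper rule still could not separate the E-scale from the behavioural programme or from time. A tidier pass mark would add little to what 15 uncontrolled before-and-after differences can show.

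**Conclusion.** No change is needed. The plan omits a significance level and an explicit rule for partial success, but it is workable as written. Read literally, efficacy requires all four outcomes, a strict standard with false success under 0.3%. An analyst would use the conventional two-sided 5% level, report four mean changes and describe a mixed result as mixed. No dosing, regulatory, go/no-go or sample-size decision hangs on Hypothesis 2c, so the exposure is the wording of one conclusion in a pilot report.

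The choice among remedies is a matter of preference: weight alone loosens the standard to 2.5%, Holm costs 9 to 12 percentage points of power for weight at d = 0.8, and restating the conjunction gains nothing. The denominator and interval for Hypothesis 1a are reporting details on a descriptive target.

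The probabilities rest on assumed equal effects, correlations of 0 to 0.7 and full completion. The mixed-result chance runs from 12% to 86% over the range shown, so it describes a possibility and does not forecast this trial. The conclusion rests on the wording of the hypothesis and the exploratory, single-group design, and does not depend on where in that range the truth lies.

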2.3.1 Does this research study involve a placebo-controlled arm?

* No

[\[reviewer notes→\]](#)

2.4 Will any research subjects be withdrawn from known effective therapy for the purpose of participating in this research study?

* No

[\[reviewer notes→\]](#)

2.5 Will screening procedures (i.e., procedures to determine research subject eligibility) be performed specifically for the purpose of this research study?

* Yes

2.5.1 List the **screening procedures that will be performed for the purpose of this research study. Do NOT include the inclusion/exclusion criteria in this section as they will be addressed in section 3; questions 3.13 and 3.14.**

A self-report questionnaire will be administered when the person first contacts us and prior to informed consent, this includes most of the screening for inclusion and exclusion criteria. When the person comes into the laboratory, and after consent, weight and height measurements will be taken, and the Center for Epidemiologic Studies Depression Scale (CES-D) and the Eating Disorder Diagnosis Scale (EDDS) will be administered. We will also ask as part of our first contact that the potential subjects obtain a doctor's note approving their participation in the study and record their diet for 3 days. The note and food record can be provided anytime up until they start the intervention. If they do not complete these two tasks they will be excluded.

[\[reviewer notes→\]](#)

2.6 Provide a detailed description of all research activities (e.g., all drugs or devices; psychosocial interventions or measures) that will be performed for the purpose of this research study.

This description of activities should be complete and of sufficient detail to permit an assessment of associated risks.

At a minimum the description should include:

- **all research activities**
- **personnel (by role) performing the procedures**
- **location of procedures**
- **duration of procedures**
- **timeline of study procedures**

Potential subjects will be screened over the phone or in person with a list of questions that may exclude them from the study. If it is determined that they are likely to be eligible, they will be asked to contact their doctor for a letter approving their participation in a weight loss program and scheduled to come to the lab where they will be consented into the study. They will also be asked to record their diet for 3 days to determine if they are willing to comply with this key component of the study. When they come into the lab, informed consent will be performed first. After the consent process is complete, subjects will be given the Center for Epidemiologic Studies Depression Scale (CES-D) and the Eating Disorder Diagnosis Scale (EDDS) to determine if they would be considered to have a current eating disorder or are currently depressed. Next the subject's weight and height will be measured in the lab by having the subjects drive onto a calibrated roll-on scale to get the weight of their chair with them in it. Then they will transfer out of their wheelchair (with assistance of the research team or trained member of our lab if requested) onto a mat table where they will be asked to lay flat on their back so that their height can be measured with a tape measure. While they are on the mat table, a member of the research team will take their chair back to the roll-on scale to weigh the chair. The subject's weight will be determined by subtracting the weight of the chair from the weight of the subject in the chair. The subject's Body Mass Index (BMI) will then be calculated. They will then transfer (or be assisted) back to their chair.

After the subjects' have been determined to be eligible, they will have their abdominal girth measured with a tape measure and their body-fat percentage will be measured with a hand-held BIA inductance measuring tool. They will also be given a demographics questionnaire and the Self-Rated Abilities for Health Practices questionnaire to answer. The LoseIt! (diet and activity journal) and E-scale apps will be installed on their phones/android devices or they will be provided with an android device with the apps already installed to use during the study. De-identified login and passwords will be provided to the subjects to use during all of the study procedures so no identifiable data will ever be collected by these apps. Some training on use of the E-scale and LoseIt! apps will be provided to the subjects as well as the first lesson of the 13-week curriculum. Over the next few days, the study team will go to all of the subject's homes to install the E-scale under their beds.

During the next 12 weeks, subjects will be asked to weigh themselves every day with the E-scale app and record their diet, exercise and weight every day with the LoseIt! app. The data that is reported in the LoseIt! app by the subjects will be monitored by the study team using the ascendapp for LoseIt!, which allows a "coach" to monitor all of the data submitted by a client. The weight loss curriculum involves weekly lessons for the participants to learn and practice things like counting calories and fat, reorganizing their kitchens, doing more cardio work around the house, etc. This curriculum was adapted from the Diabetes Prevention Program Group Lifestyle Balance (DPP GLB) curriculum at Pitt specifically for people with mobility impairments. The study team will send periodic emails with comments to the participants encouraging their progress and adherence to the protocol and lesson materials for that week. Every week at a pre-defined time, a group chat room will be conducted with all of the subject's and the research team invited to attend to go over the lesson for that week and to have a group discussion for the participants to share successes and difficulties with the group. The chat room will be hosted using Adobe Connect with the audio and video capabilities disabled. The link to the chat room for each week will be emailed to the subjects along with the lesson materials. The curriculum disbursement, progress emails, and chat rooms will be led by a dietitian/nutritionist with experience in leading group weight loss programs.

During the last week of the study (week 13). The subjects will be asked to come back to the lab in-person where their weight will again be measured using the roll-on scale. Their

abdominal girth and body-fat percentage will also be measured again. The SRAHP will be administered to the subjects again and they will also be given the final questionnaire, System Usability Scale (SUS), which will evaluate how they felt about the E-scale and some aspects of entire study. Any android devices that were loaned to the subjects during the study will be collected and the apps on their personal devices will be deleted if they wish. Over the next few days, the study team will visit all of the subject's homes to remove the E-scales or the participants can bring them with them to the lab.

If a participant indicates during the study that the E-scale they are using is malfunctioning, an investigator may talk to the participant on the phone and/or schedule a time to travel to the subjects home to troubleshoot and/or replace the E-scale with one that is working properly.

2.6.1

Will blood samples be obtained as part of this research study?

* No

*If submitting a protocol for expedited review, it should be clear that the planned blood draws are within the parameters described here:

<http://www.hhs.gov/ohrp/policy/expedited98.html> (see Expedited Research Category #2)

If **Yes**, address the frequency, volume per withdrawal, the total volume per visit, and the qualifications of the individual performing the procedure:

Study Flow Chart:

Name Flowchart	Modified Date 4/17/2017 10:46 AM
--	-------------------------------------

[\[reviewer notes\]](#)

2.7

Will follow-up procedures be performed specifically for research purposes? Follow-up procedures may include phone calls, interviews, biomedical tests or other monitoring procedures.

* No

[\[reviewer notes\]](#)

2.8

Does this research study involve the use of any questionnaires, interview or survey instruments?

* Yes

Upload a copy of all materials except for the SCID or KSADS which are on file at the IRB. The use of all instruments must be addressed in question 2.6 and/or question 2.7 (except for an exempt submission where they should be addressed on the appropriate uploaded exempt form).

Name	Modified Date
EDDS	6/24/2017 2:48 PM
Screening tool	7/17/2017 4:35 PM
Final Survey	1/29/2018 9:45 AM
CES-D	6/24/2017 2:47 PM
Demographics	6/24/2017 2:50 PM
SRAHP	6/24/2017 2:50 PM

Previously the name and publisher for commercially available materials were listed in the textbox below but effective 9/1/2015, all materials (except for the SCID and KSADS) must be uploaded using the Add button above.

[\[reviewer notes→\]](#)

2.9

If subjects are also patients, will any clinical procedures that are being used for their conventional medical care also be used for research purposes?

* n/a

If **Yes**, describe the clinical procedures (and, if applicable, their frequency) that will be used for research purposes:

2.10 The blood sample question was moved to 2.6.1.

[\[reviewer notes→\]](#)

2.11 **What is the total duration of the subject's participation in this research study across all visits, including follow-up surveillance?**

* 13 weeks

[\[reviewer notes→\]](#)

2.12 **Does this research study involve any type of planned deception?**

If Yes, you are required to request an alteration of the informed consent process (question 4.7)

* No

[\[reviewer notes→\]](#)

2.13 **Does this research study involve the use of UPMC/Pitt protected health information that will be de-identified by an IRB approved "honest broker" system?**

* No

[\[reviewer notes→\]](#)

2.14

Will protected health information from a UPMC/Pitt HIPAA covered entity be accessed for research purposes or will research data be placed in the UPMC/Pitt medical record?

* No

2.14.1

Will protected health information from a non-UPMC/Pitt HIPAA covered entity be obtained for research purposes or will research data be placed in the non-UPMC/Pitt medical record?

* No

[\[reviewer notes→\]](#)

2.15

Does this research study involve the long-term storage (banking) of biological specimens?

* No

[\[reviewer notes→\]](#)

2.16

Will research participants be asked to provide information about their family members or acquaintances?

* No

[\[reviewer notes→\]](#)

2.17

What are the main outcome variables that will be evaluated in this study?

Subjective feedback from the survey about the usefulness and participants' satisfaction with portions of the program and E-scale.

Accuracy and repeatability of the E-scale measurements

Weight change, abdominal girth change, body-fat percentage change and Self-Rated Abilities for Health Practices (SRAHP) change

2.18

Describe the statistical approaches that will be used to analyze the study data.

* Addressed below:

Since there is only one group, most outcome variables will be analyzed using summary statistics. Baseline and final measurements will also be analyzed using paired t-tests.

[\[reviewer notes→\]](#)

2.19

Will this research be conducted in (a) a foreign country and/or (b) at a site (e.g., Navajo Nation) where the cultural background of the subject population differs

substantially from that of Pittsburgh and its surrounding communities?

- * No

Note that copies of training records, licenses, certificates should be maintained in the study regulatory binder and are subject to audit by the Research Conduct and Compliance Office (RCCO).

In addition, individuals planning to conduct human subject research outside the United States must complete an optional module on the CITI training website: International Studies. [Click here](#) to access the instruction sheet for accessing optional CITI modules.

[reviewer notes→]

2.21

Will this research study be conducted within a nursing home located in Pennsylvania?

- * No

[\[reviewer notes\]](#)

Section 3 - Human Subjects

